4.2. Exclusion criteria

- Fully erupted permanent canines
- Previous orthodontic treatment.
- Canines with completed root formation

- Evidence of root resorption of adjacent teeth or root malformation of the canines that would obligate to extract any adjacent teeth or the canine(s).
- Craniofacial syndromes
- Systemic disease that would impede orthodontic treatment/surgery
- Recent exposure to radiotherapy.

4.3. Expected duration of trial

The trial will start at the first screening visit, where physical/oral examination will take place. If needed, standard radiographic screening images will be taken as well. If the patient is identified as complying with the inclusion criteria, a second visit will be programmed for the collection of standard orthodontic records and randomization for inclusion in any of the groups. The assigned interceptive treatment will start on a third visit. After a maximum of 6 months of interceptive treatment, follow up visits will be scheduled after 6, 12 and 18 months. At any of those recalls, if the canine has erupted, the patients may opt to start regular orthodontic treatment with fixed appliances if needed or desired (average duration of 24 months) and a last follow up visit will be programmed after the end of this treatment for evaluation of the final canine position.

5. Trial Procedures

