Patients in **Subgroup nCLA**, constituting patients with no cross bite present but lacking space for adequate tooth alignment in the dental arch, will be randomly attributed to one of our three usual treatment options, being interceptive maxillary expansion (IME), extraction of the deciduous canines (EXIII), or no treatment (CO). The latter will constitute the control group within Group nCLA, indicative for maxillary permanent canine eruption in case of lack of space in the dental arch. After this interceptive treatment, all the patients will be enrolled in a standard follow up protocol. In case of absence of deciduous maxillary canines, randomization will not be possible. These patients will still be treated with expansion because of the lack of space and will also be enrolled in subsequent follow-up.

Patients in **Subgroup nCLB** will also be randomly attributed to one of these three usual treatment protocols, being interceptive maxillary expansion (IME), extraction of the deciduous canines (EXIII), or no treatment (CO). The latter will constitute the control group within Subgroup nCLB. After this interceptive treatment, all the patients will be enrolled in a standard follow up protocol. In case of absence of deciduous maxillary canines, randomization will not be possible. These patients will still be treated with expansion because of the lack of space and will also be enrolled in subsequent follow-up.

Subgroup nCLC, constituting the patients with no cross bite present but lacking space for adequate tooth alignment in the dental arch and with very badly positioned and angulated permanent maxillary canine(s), will receive interceptive maxillary expansion (IME) using the standard expansion techniques described above and commonly applied in the university hospital. Patients in Subgroup nCLC, after receiving interceptive expansion treatment, will be further subjected to extraction of the deciduous canine at 6month follow-up, whenever still present in the dental arch, as well as, depending on the severity of canine angulation and position, of the first deciduous molar. Decision for extraction of one or both of these deciduous teeth will be the responsibility of the treating dentist who will have to evaluate the clinical circumstances presenting in this patient with

very badly positioned permanent maxillary canines. Sequence of eruption other than 3-4-5 will also constitute a criterion for extraction of these deciduous teeth.

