After this interceptive treatment, which will last for a maximum of 6 months, all patients will be enrolled in a standard follow up protocol, requiring a minimum of 3 recall visits at 6, 12 and 18 months.

[figure not shown]
2. Non cross bite group with normal adequate space.

Accordingly, Group nCN will constitute all other eligible patients, consecutively seen at the first consultation of the Department of Orthodontics, with one/two impacted permanent maxillary canines without cross bite and showing normal adequate space in the dental arch for tooth alignment. Also these subjects will be categorized into the three subgroups A, B and C. They will receive no interceptive treatment (CO) at all except for subgroup nCNC, constituting of patients with normal alignment and adequate amount of space present but presenting with very badly positioned and angulated permanent maxillary canines. They will be further subjected to extraction of the deciduous canine (EX-III), whenever still present in the dental arch, as well as, depending on the severity of canine angulation and position, of the first deciduous molar (EX-IV). Decision for extraction of one or both of these deciduous teeth will be the responsibility of the treating dentist who will have to evaluate the clinical circumstances presenting in this patient with very badly positioned permanent maxillary canines. Sequence of eruption in the maxilla other than 3-4-5 (canine, first and second premolar) will also constitute a criterion for extraction of these deciduous teeth

After this intervention, all patients in this Subgroup nCN will be enrolled in a standard follow up protocol, requiring minimum one recall visit at 12 months for follow up of normal eruption, eventually a second one after 24 months, provided the maxillary permanent canine is not erupted yet, its root is still not completely formed and no other orthodontic treatment needs are present.

All subjects included in this trial will eventually be subjected to the described follow up procedures, which are described in more detail in Chapter 5. The follow up procedure is designed in order to detect positional changes of the permanent canine position, either spontaneous changes in the control group or changes associated with the interceptive measures taken. Follow up is a necessary and standard procedure for pointing out impacted canines and their true indication for surgical exposure of this tooth.

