5.1. By visit

Screening visit

Patients come to our service seeking orthodontic advice. After physical/oral examination, a panoramic radiograph will be taken if considered necessary. Patients needing interceptive treatment and complying with the selection criteria will be identified.

Second Visit (Record taking)

Clinical photographs and orthodontic study casts, constituting normal orthodontic records for adequate diagnostics and treatment planning will be taken, as well as a standard long cone apical radiograph (LCAR) to determine the position of the canine. Depending on the obtained parameters related to canine position and angulation, the patient will be included in one of the groups detailed in chapters 3 and 4. The patient and parents will be informed about the need for treatment and they will be asked for consent when using the data for the purposes of the study. They will be given the informed consent, included in our regular contract for orthodontic treatment, with all the necessary details and information.

Third visit

If the patient decides to start treatment, the assigned treatment option will start (expansion, extraction of deciduous canine/molar or no treatment). Patients in the expansion group will be in treatment during a maximum of 6 months taking on average 4 and maximum 6 consultations. After

interceptive treatment with a removable expansion appliance, it might be necessary to wear the modified removable appliance at night for an extended period of 2 months.

Follow up 6 months

- If the canine has erupted, a reevaluation of the specific presenting malocclusion will be performed and the need for further orthopedic or fixed appliance treatment will be discussed with the patient or his/her parents/guardians. Normal orthodontic treatment can be performed if desired. Only at the end of orthodontic treatment or, in case of no treatment need, at the end of late mixed dentition transition into permanent dentition, a last follow up visit will be planned in order to evaluate the end result.
- If the canine has not erupted yet, a long cone apical radiograph will be taken for evaluation of the canine position and reevaluation will take place after 6 months (= follow up visit 12 months).

Follow up 12 months

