- If the canine has not erupted yet, and positive progress was monitored at the 12 months follow up visit, a new LCAR will be taken to reevaluate canine eruption process, unless clear clinical indicators are present witnessing successful path of eruption, i.e. clear bulging of the canine crown in the vestibulum or clear canine cusp morphology visible in the buccal mucosa. Patient will then be instructed to report for follow up appointment at the time of canine eruption into the dental arch or at the latest after 6 months, being an extra 24 months recall. Anyhow, at the 18 months follow up visit, a reevaluation of the specific presenting malocclusion will be performed and the need for further orthopedic or fixed appliance treatment will be discussed with the patient or his/her parents/guardians. Normal orthodontic treatment can be performed if desired or needed at the time. In this case, further spontaneous canine eruption will be monitored during orthodontic treatment. Only at the end of this orthodontic treatment or, in case of no further treatment need, at the end of late mixed dentition transition into permanent dentition, a last follow up visit will be planned in order to evaluate the end result.

Follow up End result

As indicated above, two aspects of interceptive orthodontic treatment will be monitored. First of all the process of canine eruption being the maxillary permanent canine perforating the oral mucosa and erupting into the dental arch, and second the final position of the canine in the dental arch and its occlusion. Evaluation of the final result, eventually after orthodontic treatment, will include esthetics as well as functional occlusion and periodontal parameters giving an indication of gingival health. Assessment of the following parameters will be made: final position of the canine, final occlusion, root integrity of the canine and adjacent teeth, level of gingiva, general esthetic and functional result, gingival health. In order to do this, routine final records (clinical pictures, casts, LCAR or panoramic radiographs) will be taken as is performed for evaluation of standard orthodontic treatment.

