8.1. Sample size

Randomisation into expansion, extraction and control will be applied for patients without cross-bite having lack of space and – based on canine position and angulation - belonging to strata nCLB and nCLA. Within each of both strata, a randomisation will be performed using permuted blocks of varying size, yielding an equal number of patients in each of the three groups.

Success of the approach is defined as eruption without necessity of surgical intervention and integrity of the roots of the adjacent teeth. The primary endpoint is defined as the percentage success after 18 months. The trial is powered to show a difference between any of the pairs of groups. To have at least 80% power to show a higher success rate in one group compared to the other group, there are 78 subjects needed in each group assuming a success rate of 50% in the first group and 75% in the second group. The calculation is based on a two-sided χ^2 -test with alpha set at $0.05/3=0.0167$ to control the family-wise error rate at 5% (3 pairwise comparisons). However, to increase the amount of information for the development of a prediction model for success at 18 months (cfr. second aim of the study) it has been decided to increase the number of patients to 100 per group (300 patients in total).

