8.2. Analysis

The analysis of the primary endpoint will be based on a stratified χ^2 -test using a Bonferroni-Holm correction to correct for multiple testing (the strata are nCLB and nCLA). The same approach will be used for the comparison at the earlier timepoints (6 and 12 months). No interim analyses are planned, neither for efficacy, nor for futility. The analysis will be performed on an intent-to-treat basis.

A multivariable logistic regression model will be used to predict maxillary permanent canine impaction (=lack of success) on all included subjects. A backward selection procedure will be applied with 0.157 as critical level for the p-value. This critical value corresponds to the use of the Aikake Information Criterion (AIC) for model selection. With AIC we require that the increase in model χ^2 has to be larger than two times the degrees of freedom. This strategy provides a trade-off between erroneous inclusion and exclusion of covariates in a prediction model (Sauerbrei W. The use of resampling methods to simplify regression models in medical statistics. *Applied Statistics* 1999;48 (3):313–329.). The considered predictors are: strata formed by presence of cross-bite and parameters related to canine position and angulation, non-eruption, interceptive strategy, patient's age, stage of canine root formation, premature loss of deciduous teeth, familial history, space deficiency (arch length discrepancy).

As a sensitivity analysis, the prediction model will also be applied separately on the patients from the randomized and non-randomized part of the study.

9. Quality assurance

During this randomized clinical trial only standard operating procedures will be employed, such as i.e. removable expansion device, fixed expansion device, headgear, etc.. They are all validated, thoroughly described and widely used techniques. It will be up to the treating professional to decide for a given case which procedure to follow, in line with existing traditions in the specific collaborating centres. However, the main purpose should be attained which is expansion or in other words gaining extra space for tooth alignment. Depending on the interceptive treatment to be accomplished, decision will be taken to employ one specific treatment protocol to reach the goal set forward.

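### The 18-month primary endpoint has no stated time origin; if visits are counted from the end of treatment, as the prose suggests, the randomised expansion arm is assessed up to 6 months later than extraction and control

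*Combined protocol and SAP*

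**What the plan says.** Section 8.1: "The primary endpoint is defined as the percentage success after 18 months". Success means eruption without surgery and with intact roots of the adjacent teeth. Neither 8.1 nor 8.2 gives the starting point of the 18 months. Section 5.1 and the flowchart (3.6) label the visits 6, 12 and 18 months, also without an origin.

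Three places describe when follow-up begins:

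- Section 3.4, separately for nCLA and for nCLB, the two randomised strata: "After this interceptive treatment, all the patients will be enrolled in a standard follow up protocol".
- Section 3.4, at the end of the lack-of-space text: "After this interceptive treatment, which will last for a maximum of 6 months, all patients will be enrolled in a standard follow up protocol".
- Section 4.3, for the whole trial: "After a maximum of 6 months of interceptive treatment, follow up visits will be scheduled after 6, 12 and 18 months".

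The synopsis likewise lists the maximum treatment duration (6 months) and the follow-up duration (6-18 months) as separate items.

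The randomised arms are expansion, extraction of the deciduous canines, and no treatment. Only expansion has a duration. Section 5.1: "Patients in the expansion group will be in treatment during a maximum of 6 months". Treatment starts at the third visit. On the analysis, section 8.2 says "The analysis will be performed on an intent-to-treat basis", and it applies the primary method to the 6- and 12-month comparisons as well.

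**The concern.** The endpoint is a yes/no outcome that depends on how long the canine has had to erupt. A randomised comparison is fair only if the arms are assessed after the same elapsed time. If the months are counted from the end of treatment, the clock starts up to 6 months later for expansion than for the other two arms, and part of any observed difference would be extra observation time.

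The protocol itself expects eruptions in the months at stake. A canine that is progressing but unerupted at 18 months is asked back on eruption or "at the latest after 6 months, being an extra 24 months recall".

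Two errors are possible. Expansion could be declared better when it is not, or a true advantage of extraction over expansion could be hidden. The 6- and 12-month comparisons would be exposed in the same way. Sites could also use different clocks, because the trial is multicentre and section 9 leaves the expansion technique to each centre.

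**Working it through.** **1. The plan's own figure.** Inputs from 8.1: 50% v 75%, two-sided alpha 0.05/3 = 0.0167, power 80%.

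n = [z(1−α/2)·√(2p̄(1−p̄)) + z(0.80)·√(p₁(1−p₁) + p₂(1−p₂))]² / (p₂−p₁)², with p̄ = 0.625

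n = [2.394 × √0.46875 + 0.842 × √0.4375]² / 0.0625 ≈ 77.1, rounded up to 78 per group.

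This matches the plan. Power at 100 per group is 90.3%. The sample size is not in question.

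**2. Elapsed time from the third visit to the 18-month assessment, counted from the end of treatment.**

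| Arm | Treatment lasts | Assessment falls at |
|---|---|---|
| Expansion | 0 to 6 months | 18 to 24 months |
| Extraction | brief procedure (assumed) | about 18 months |
| Control | none | 18 months |

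The gap is therefore 0 to 6 months. Six months is a stated maximum, and no average duration is given. Counted from the third visit in all arms, the gap is 0.

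**3. What a gap could do.** The documents give no eruption rate over time, so this step is an illustration. Assume no true treatment effect, 50% success at 18 months (the lower rate in 8.1) and a constant eruption rate, so that success at t months = 1 − 0.5^(t/18). The planned analysis was simulated with 200,000 trials, 100 per arm, 50 per stratum (assumed split), a Mantel-Haenszel chi-square without continuity correction, and Holm over the three pairs.

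| Gap (months) | Apparent success, expansion v others | At least one false positive |
|---|---|---|
| 0 | 50.0% v 50.0% | 4.8% |
| 2 | 53.7% v 50.0% | 7.6% |
| 3 | 55.5% v 50.0% | 11% |
| 4 | 57.1% v 50.0% | 16% |
| 6 | 60.3% v 50.0% | 30% |

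At the maximum gap the artefact is 60.3 − 50.0 = 10.3 points, or 10.3/25 = 41% of the difference the trial is powered for.

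**4. Without the constant rate.** Suppose a fixed share of the canines not successful at 18 months erupts in the extra time. At 5%, expansion shows 50 + 0.05 × 50 = 52.5% and the false-positive chance is about 6%. At 10%, it shows 55% and the chance is about 10%.

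**5. The opposite error.** Suppose expansion truly reaches 50% and extraction 75% at 18 months. With the maximum gap expansion would show 60.3%. Power for that pair at alpha 0.0167 and 100 per group falls from 90.3% to about 43%.

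**6. Earlier time points, same assumptions as step 3.** With a 3-month gap the false-positive chance is about 15% at the 12-month comparison and 26% at the 6-month comparison. With the maximum gap it is 45% and 73%.

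**The case against.** The strongest reply is that a common clock may be intended, and several features of the text allow it:

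- The flowchart runs from the third visit straight to the 6-month follow-up, with no end-of-treatment visit.
- In nCLC, extraction follows expansion of up to 6 months and takes place at the 6-month follow-up, which fits a clock started at treatment.
- Section 3.4 says that nCLA and nCLB patients enter follow-up after treatment, not that months are counted from that day.
- The section 3.4 sentence with the 6-month maximum directly follows the text on the non-randomised nCLC subgroup, although it refers to all patients.
- Section 4.3 could mean a fixed 6 months in every arm, which also gives no gap.
- The figure in 3.4 and the study diagram in 3.5 could not be read in the text available and may state an origin.

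This stands. A reader might infer that the plan does assess expansion 6 months late; the documents do not establish that. They show an unstated origin, with wording that leads to unequal timing if followed literally.

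The size is also open to challenge. The 30% figure needs every expansion patient to use the full 6 months, and the eruption model is assumed. It ignores that canines exposed after the 12-month visit are already failures and cannot erupt later, so it tends to overstate the gain between 18 and 24 months. This stands too, and is why the result is given as a range from no effect.

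A reader might further infer that the surgery rule adds to the bias towards expansion. The trigger is an unchanged position between two visits 6 months apart, and nothing in the documents shows that a later window yields fewer such canines. The direction through root integrity is likewise not established.

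**Conclusion.** The point holds as a defect of definition with a conditional bias. The readable text gives no origin for the visits or the primary endpoint. The sentences that describe timing, including those for the randomised strata, place follow-up after treatment. Followed that way, expansion is assessed up to 6 months later than extraction and control, which tends to favour expansion through eruption.

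The size ranges from nothing, under a common clock, to a family-wise error of about 30% at the maximum gap. Intermediate gaps of 2 to 4 months give about 8% to 16%. All these rates rest on the assumed success rate and eruption pattern; none is a prediction for this trial. The ambiguity should be removed because it touches the primary comparison and different sites could resolve it differently.

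**What to change.** Add to 8.1 and 4.3: in nCLA and nCLB, the 6-, 12- and 18-month assessments and the primary endpoint are timed from the date of randomisation in all three arms. Align the follow-up sentences in 3.4 and the sentence in 4.3, and state there, as 5.1 does, that the 6-month maximum refers to expansion. Randomisation is a better origin than treatment start: every intent-to-treat patient has that date, whereas under 5.1 treatment starts at the third visit only if the patient decides to go ahead.

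The sample size and the test in 8.2 do not change, and no visit or patient is added. If a common clock from the third visit was always meant, the edit mainly makes it explicit and moves the origin to the randomisation date.

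There is a clinical cost if sites would otherwise count from the end of treatment. Expansion visits, including the 12-month decision on CBCT and exposure, then come up to 6 months earlier relative to the end of expansion. After a full 6 months of expansion, that decision falls about 12 − 6 = 6 months after expansion ends. The 6-month visit may fall at the end of active expansion or during the 2 months of night wear. The investigators should judge whether this is acceptable. If they prefer the later surgical review for expansion, they can schedule the extraction and control visits at the same elapsed time since randomisation.

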5.1. By visit

Screening visit

Patients come to our service seeking orthodontic advice. After physical/oral examination, a panoramic radiograph will be taken if considered necessary. Patients needing interceptive treatment and complying with the selection criteria will be identified.

Second Visit (Record taking)

Clinical photographs and orthodontic study casts, constituting normal orthodontic records for adequate diagnostics and treatment planning will be taken, as well as a standard long cone apical radiograph (LCAR) to determine the position of the canine. Depending on the obtained parameters related to canine position and angulation, the patient will be included in one of the groups detailed in chapters 3 and 4. The patient and parents will be informed about the need for treatment and they will be asked for consent when using the data for the purposes of the study. They will be given the informed consent, included in our regular contract for orthodontic treatment, with all the necessary details and information.

Third visit

If the patient decides to start treatment, the assigned treatment option will start (expansion, extraction of deciduous canine/molar or no treatment). Patients in the expansion group will be in treatment during a maximum of 6 months taking on average 4 and maximum 6 consultations. After

interceptive treatment with a removable expansion appliance, it might be necessary to wear the modified removable appliance at night for an extended period of 2 months.

Follow up 6 months

- If the canine has erupted, a reevaluation of the specific presenting malocclusion will be performed and the need for further orthopedic or fixed appliance treatment will be discussed with the patient or his/her parents/guardians. Normal orthodontic treatment can be performed if desired. Only at the end of orthodontic treatment or, in case of no treatment need, at the end of late mixed dentition transition into permanent dentition, a last follow up visit will be planned in order to evaluate the end result.
- If the canine has not erupted yet, a long cone apical radiograph will be taken for evaluation of the canine position and reevaluation will take place after 6 months (= follow up visit 12 months).

Follow up 12 months

- If the canine has erupted, a reevaluation of the specific presenting malocclusion will be performed and the need for further orthopedic or fixed appliance treatment will be discussed with the patient or his/her parents/guardians. Normal orthodontic treatment can be performed if desired. Only at the end of orthodontic treatment or, in case of no treatment need, at the end of late mixed dentition transition into permanent dentition, a last follow up visit will be planned in order to evaluate the end result.
- If the canine has not erupted yet, a long cone apical radiograph will be taken for evaluation of the canine position.
 - If a difference in vertical position is found when comparing with the LCAR taken during the last follow up visit, showing positive progression in canine eruption, reevaluation will take place after 6 months (= follow up visit 18 months).
 - If canine position between 6 and 12 months follow up remains unchanged, a CBCT might be indicated to evaluate canine position and its relation to the neighboring teeth. Depending on the CBCT evaluation, it might be decided to surgically expose the canine, either via a closed or open technique depending on its position. When the canine is exposed, further active orthodontic treatment will be needed to guide the canine into its position in the dental arch. Only at the end of orthodontic treatment, a last follow up visit will be planned in order to evaluate the end result, being the final position of the maxillary permanent canine in the dental arch.

Follow up 18 months

- If the canine has erupted, a reevaluation of the specific presenting malocclusion will be performed and, in case this should not have been made already, the need for further orthopedic or fixed appliance treatment will be discussed with the patient or his/her

parents/guardians. Normal orthodontic treatment can be performed if desired. Only at the end of orthodontic treatment or, in case of no treatment need, at the moment the canine reaches its final position in the dental arch, a last follow up visit will be planned in order to evaluate the end result.

- If the canine has not erupted yet, and positive progress was monitored at the 12 months follow up visit, a new LCAR will be taken to reevaluate canine eruption process, unless clear clinical indicators are present witnessing successful path of eruption, i.e. clear bulging of the canine crown in the vestibulum or clear canine cusp morphology visible in the buccal mucosa. Patient will then be instructed to report for follow up appointment at the time of canine eruption into the dental arch or at the latest after 6 months, being an extra 24 months recall. Anyhow, at the 18 months follow up visit, a reevaluation of the specific presenting malocclusion will be performed and the need for further orthopedic or fixed appliance treatment will be discussed with the patient or his/her parents/guardians. Normal orthodontic treatment can be performed if desired or needed at the time. In this case, further spontaneous canine eruption will be monitored during orthodontic treatment. Only at the end of this orthodontic treatment or, in case of no further treatment need, at the end of late mixed dentition transition into permanent dentition, a last follow up visit will be planned in order to evaluate the end result.

Follow up End result

As indicated above, two aspects of interceptive orthodontic treatment will be monitored. First of all the process of canine eruption being the maxillary permanent canine perforating the oral mucosa and erupting into the dental arch, and second the final position of the canine in the dental arch and its occlusion. Evaluation of the final result, eventually after orthodontic treatment, will include esthetics as well as functional occlusion and periodontal parameters giving an indication of gingival health. Assessment of the following parameters will be made: final position of the canine, final occlusion, root integrity of the canine and adjacent teeth, level of gingiva, general esthetic and functional result, gingival health. In order to do this, routine final records (clinical pictures, casts, LCAR or panoramic radiographs) will be taken as is performed for evaluation of standard orthodontic treatment.

